1.4 Somatostatin Receptor Targeted Therapy

Known as peptide receptor radionuclide therapy (PRRT), this molecularly targeted internal radiation has been utilized in Europe for nearly 20 years. The two main radiopharmaceutical agents are ^{90}Y -DOTATOC and ^{177}Lu -DOTATATE, both targeting sstr2. The response rates are very similar with very few complete responses, 20-30% partial responses, and greater than 50% stable disease among patients who have progressed on other therapies^{22,23}. The time to progression following PRRT, for these patients with progressive metastatic neuroendocrine tumors has been 36-48 months compared to 5-7 months with everolimus or sunitinib^{24,25}.

The normal organ at greatest risk for toxicity with ^{90}Y -DOTATOC is the kidney^{21,23,26,27}. In our previous Phase II trial in adults and our Phase I trial in children, we were able to decrease renal toxicity with amino acid infusion and hydration^{13,21,28}. This trial is designed to utilize dosimetry to maximize radiation dose to tumor while minimizing renal toxicity.

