6.0 Imaging and Treatment Plan

**Phase II,
Dosimetry-Guided, Peptide Receptor Radiotherapy (PRRT) with
⁹⁰Y-DOTA-tyr³-Octreotide (⁹⁰Y-DOTATOC) in Children and Adults
with Neuroendocrine and other Somatostatin Receptor Expressing Tumors**

Treatment Cycles and Followup		Imaging and Treatment Schedule	Initial ⁹⁰ Y-DOTATOC Dose	Cumulative ⁹⁰ Y-DOTATOC Dose	Cumulative Renal Radiation
Cycle 1 Week 1	Day 1	Physical exam with height, weight, vitals, labs, list, GFR, pregnancy test; QOL questionnaire Start 18 hrs IV/PO fluids			
	Day 2	⁹⁰ Y-DOTATOC + IV amino acids Continue IV/PO fluids for 48 hrs	50 mCi/m ² in children; 120 mCi in adults	120 mCi maximum	
	Day 4	⁹⁰ Y-DOTATOC PET/CT			
Cycle 2 Week 7-9	Day 1	Physical exam with height, weight, vitals, labs, med list, GFR, pregnancy test Start 18 hrs IV/PO fluids			
	Day 2	⁹⁰ Y-DOTATOC + IV amino acids Continue IV/PO fluids for 48 hrs	Dosimetry determined	270 mCi maximum	
	Day 4	⁹⁰ Y-DOTATOC PET/CT			
Cycle 3 Week 13-17	Day 1	Physical exam with height, weight, vitals, labs, list, GFR, pregnancy test Start 18 hrs IV/PO fluids			
	Days 2-3	⁹⁰ Y-DOTATOC + IV amino acids Continue IV/PO fluids for 48 hrs	Dosimetry determined	420 mCi maximum	≤ 23 Gy
FU	3 months after treatment 3	Physical exam with height, weight, vitals, labs, med list, GFR; QOL questionnaire, diagnostic CT (MRI)			
	6-9 months after treatment 3	Physical exam with height, weight, vitals, labs, med list, GFR; diagnostic CT (MRI) ⁶⁸ Ga-DOTATOC PET/CT;			

Treatment consists of 3 cycles, 6-8 weeks apart. Cycle 1 dose is fixed. Cycles 2 and 3 doses will be determined by dosimetry-based calculation of renal doses from previous cycles; total renal dose ≤ 23Gy.

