7.0 Calendar of Tests and Procedures

Calendar of Tests and Procedures									
Test	Base line ⁶	C1D1 ⁷	C1D2	C2 D1	C2D2	C3D1	C3D2	3-4 Month Followup ^{8, 11}	6-9 Month Followup
Physical Exam	X	X		X		X		X	X
Medical history/treatment history	X	X							
Vital signs ¹	X	X	X	X	X	X	X	X	X
Medication list	X	X		X		X		X	X
GFR if indicated ²	X	X		X		X		X ¹²	X
Blood Tests ³	X	X	X ¹⁴	X	X ¹⁴	X	X ¹⁴	X	X
QOL questionnaire	X	X						X ¹³	
Pregnancy Test ⁴	X	X ⁹	X ⁹	X	X ⁹	X	X ⁹		
⁶⁸ Ga-DOTATOC (TATE) PET/CT	X								X
Diagnostic CT or MRI	X							X	X
⁹⁰ Y-DOTATOC Therapy (& Amino Acids)			X		X		X		
Skin assessment ¹⁵			X		X		X		
Dosimetry (blood & imaging)			X		X		X		
Adverse Event Assessment	X ⁵	X	X	X		X		X	X
Fluid diary ¹¹		X	X	X	X	X	X		

1. temp, pulse, respirs, b/p, weight. Height at baseline only. Weight at baseline and Day 1 of each cycle.

2. required for children(<18 years). Required for adults (18 and older) if serum creatinine >1.2mg/dl. If required at baseline for patient, then all subsequent time points require nuclear GFR also.

3. blood tests include: CBC/diff, AST, ALT, creatinine, plus urinalysis at baseline only and T.Bili at baseline only.

4. required for females of child bearing potential only

5. Documentation of baseline symptoms

6. All baseline evaluations within 30 days of first ⁹⁰Y-DOTATOC dose except blood tests need to be within 10 days and ⁶⁸Ga-DOTATOC/TATE PET/CT needs to be within 6 months of first ⁹⁰Y-DOTATOC infusion. The diagnostic scans need to be within 120 days of the first ⁹⁰Y-DOTATOC infusion.

7. events only repeated prior to treatment 1 if they fall outside of the baseline windows noted in footnote 6.

8. Patients who discontinue dosing of ⁹⁰Y-DOTATOC early and who have received at least 1 dose of ⁹⁰Y-DOTATOC are also required to complete follow up appointments per calendar

9. repeat testing can be point of care urine pregnancy test done in Nuclear Medicine.
10. Patients will be instructed to have fluid intake of 1.5 liters Day 1 and 2 liters/day on Days 3 & 4.
11. 3-4 month follow up procedures may be performed by patient's local MD.
12. If GFR is indicated, patients will be required to return to UIHC.
13. If patient does not return to UIHC for F/U, QOL may be mailed or e-mailed to patient.
14. Electrolytes will be drawn during the last hour of amino acid infusion.
15. The skin at the site of the infusion will be assessed by clinic visit or phone at 3-5 days following each infusion of amino acids.

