8.0 Duration of Therapy and Stopping Rules

8.1 Stopping Rules for individual subject

In the absence of treatment delays due to adverse events, treatment may continue for 3 cycles or until one of the following criteria applies:

- Cumulative renal radiation dose exceeds 23 Gy.
- Intercurrent illness prevents further administration of treatment.
- Unacceptable adverse event(s) such as irreversible renal or hematopoietic toxicity.
- Initiation of another tumor specific therapy.
- Patient decides to withdraw from the study.
- General or specific changes in the patient's condition render the patient unacceptable for further treatment in the judgment of the investigator.

Other causes of discontinuation from study:

- Termination of study by Sponsor.
- Subject's condition no longer requires study drug.

* Note: Disease progression alone does not mandate discontinuation of ⁹⁰Y treatment.*

Disease progression per RECIST 1.1 criteria during the follow up period will warrant removal from study.

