9.1 Adverse Events List and Reporting Requirements

As with any new drug, this study may involve risks that are currently unforeseeable. The most frequent adverse events observed in adults treated with these drugs are listed below.

Severity of adverse events will be graded according to NCI Common Terminology Criteria for Adverse Events version 4.0 (CTCAE v4.0) which is available at <http://ctep.cancer.gov/reporting/ctc.html>.

Adverse events will be collected from time of consent until 30 days post ⁹⁰Y treatment. Labs will only be collected as adverse events if deemed clinically significant by the investigator. Serious Adverse Events (SAE's) that occur >30 days after the last ⁹⁰Y treatment will only be reported if at least possibly related to investigational product.

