10.3 Concomitant Therapy

The subject may not receive any other approved or investigational anti-neoplastic therapies for the treatment of the refractory somatostatin-receptor positive tumor during the course of the study, excluding somatostatin analogues and bisphosphonates. However, all subjects on somatostatin analogue therapy will discontinue therapy from 12 hours prior to a) injection with ^{68}Ga -DOTATOC, and b) infusion with ^{90}Y -DOTA-tyr³-Octreotide until 12 hours post administration. Subjects who have been on hormonal therapy (other than somatostatin analogues) for ≥ 2 months with SD or PD may continue to receive hormonal therapy during this study. Subjects who initiate another tumor-specific therapy will be discontinued from further treatment with ^{90}Y -DOTA-tyr³-Octreotide. Patients may continue long acting Somatostatin analogues between cycles of ^{90}Y therapy. It should be administered as standard of care after completion of dosimetry imaging for Cycles 1 and 2. Following Cycle 3, it may be given on Day 3 or later. Patients on long acting Lanreotide should have this treatment held until after ^{90}Y treatment Cycle 3. Short acting somatostatin analogue can be used at the discretion of the treating physician to bridge the patient.

All subjects who have received at least one dose of ^{90}Y -DOTA-tyr³-Octreotide must continue into the Long-Term Follow-up Study Period at the point of treatment discontinuation. This is necessary to determine any long-term effects of treatment with ^{90}Y -DOTA-tyr³-Octreotide.

Subjects may receive, at the discretion of the investigator, appropriate medical treatment for medical problems that arise while on study.

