Treatment efficacy, defined as a complete response, partial response or stable disease (CR+PR+SD), is the primary endpoint of interest in this dosimetry-guided Phase II trial. Tumor response will be defined according to RECIST1.1 criteria applied on up to five target lesions (primary tumor if not surgically removed, up to two liver lesions, up to two nodal metastases, metastatic lesion in other organs, such as ovary, breast) that will be quantified and compared between pre-therapy and 3-9 months post-therapy high-resolution, contrast-enhanced CTs. Osseous metastases may be followed as non-target lesions. ⁹⁰Y-DOTATOC will be deemed worthy of further study if its associated response rate is ≥ 0.60 , and clinically uninteresting if its rate is ≤ 0.40 . Enrollment will proceed according to an optimal Simon two-stage study design. Sixteen (16) subjects will be enrolled in the first stage; if 7 or fewer patients respond, the arm will be closed and the treatment ruled clinically uninteresting. Otherwise, an additional 30 subjects will be enrolled. If 24 or more responses are observed in the total of 46 subjects, then the treatment will be ruled worthy of further study. The study design has a probability of early termination equal to 0.72. Power to detect efficacy is 0.80 with a type 1 error rate of

0.05.

Secondary analysis will focus on time to tumor progression and overall survival. The method of Kaplan- Meier will be used to estimate progression and survival rates. Subjects for whom the outcome of interest is not observed at the 6 month follow-up will be treated as censored observations in the survival analysis.

12.2 Primary Objective 2

Adverse events will be recorded and reported in tabular form by type and grade. If four or more subjects experience renal toxicity \geq Grade 4, the radiopharmaceutical will be declared too toxic and the trial will be stopped. If any other irreversible Grade 4 toxicity is observed in four or more subjects, the treatment will be declared too toxic and will be stopped. Adverse events will be graded according to the most recent CTE guidelines.

12.3 Secondary Objective 1

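### Progression in follow-up removes subjects from study and nothing continues vital status afterwards; if removal ends ascertainment, the Kaplan-Meier overall survival in 12.1 is biased upward, modestly

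*Combined protocol and SAP*

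**What the plan says.** Section 12.1 names time to tumor progression and overall survival as secondary analyses, estimated by Kaplan-Meier. Its only censoring rule is "Subjects for whom the outcome of interest is not observed at the 6 month follow-up will be treated as censored observations".

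Section 8.1, on stopping rules for the individual subject, adds: "Disease progression per RECIST 1.1 criteria during the follow up period will warrant removal from study". It does not mention survival or vital status.

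Section 10.3 says that all subjects given at least one dose "must continue into the Long-Term Follow-up Study Period at the point of treatment discontinuation". The reason given is "This is necessary to determine any long-term effects of treatment" with the study drug. No content, schedule or duration for that period appears anywhere.

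The section 7.0 calendar ends at the 6-9 month visit and has no vital-status item. Footnote 8 says that subjects who stop dosing early "are also required to complete follow up appointments per calendar". That covers stopping treatment, not removal from study. Under 9.1, serious adverse events more than 30 days after the last treatment "will only be reported if at least possibly related to investigational product".

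**The concern.** Progression is the event most likely to precede death in this population. If subjects leave at progression and nobody records whether they are alive, the survival analysis drops them just as their risk probably rises. Kaplan-Meier then treats them as if they shared the prospects of those who remain.

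Sections 8.1 and 10.3 can be read as entry into long-term follow-up and later exit from it. On that reading, however, progressors leave before the long-term effects that 10.3 wants can be seen. Two teams applying this text in good faith could follow progressors differently and report different survival curves. Deaths that are not recorded at the time may be hard to recover later.

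**Working it through.** **The plan's own figures.** The only computable figures in 12.1 belong to the primary two-stage design (stop at 7 or fewer of 16; success at 24 or more of 46). Exact binomial calculation gives early termination 0.716 at a rate of 0.40 (stated 0.72), power 0.801 at 0.60 (stated 0.80) and type 1 error 0.049 (stated 0.05). The design reproduces and does not involve survival. No survival rate, event count or precision is stated, so the size of the problem has to be illustrated.

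**Inputs from the documents**
- Time to progression after this class of therapy: "36-48 months compared to 5-7 months with everolimus or sunitinib" (1.4). The first range is the one for this therapy. The text does not say whether it is a median, and 13.3 speaks of a mean above 4 years.
- Cycle 3 in week 13 to 17 (schema and 6.0), which is 2.99 to 3.91 months from first dose.
- CT or MRI only at baseline, at 3-4 months and at "6-9 months after treatment 3". Removal would therefore usually take effect at the 3-4 month scan.

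**Assumptions.** Exponential times; no deaths without documented progression; median survival after progression of 6, 12 or 24 months; removal ends ascertainment.

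**Formulas.** Let a be the progression rate and b the death rate after progression, each ln 2 / median. V1 is the 3-4 month scan and V2 the horizon, both from first dose.
- True survival: S(t) = exp(-at) + [a/(b - a)] × [exp(-at) - exp(-bt)], taken at V2.
- With progressors censored at V1, Kaplan-Meier estimates S(V1) × S(V2 - V1).
- Share removed: S(V1) - exp(-a·V1).

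**Worked case.** Medians of 36 months to progression and 12 months afterwards; Cycle 3 at week 17; scan at 3 months and horizon at 6 months after Cycle 3.
- V1 = 6.91, V2 = 9.91; a = 0.01925, b = 0.05776, so a/(b - a) = 0.5.
- True: 0.8263 + 0.5 × (0.8263 - 0.5642) = 0.957.
- Estimated: S(6.91) × S(3.00) = 0.9777 × 0.9954 = 0.973.
- Overstatement: 1.6 points.
- Removed: 0.9777 - 0.8754 = 0.102, or 4.7 of 46 subjects.
- Standard error at n = 46: √(0.957 × 0.043/46) = 3.0 points.

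With the scan at 4 months and the horizon at 9 months after Cycle 3 (V1 = 7.91, V2 = 12.91), the same medians give 0.933 true against 0.960 estimated, or 2.7 points. A simulation of 4,000 trials of 46 subjects in that setting gave means of 0.932 with full follow-up and 0.959 with removal.

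**Ranges of overstatement, in percentage points**

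| Time to progression | Survival after progression | 6 months after Cycle 3 | Across the 6-9 month window |
|---|---|---|---|
| 36-48 months as median | 6-24 months | 0.5-2.4 | 0.5-4.0 |
| 36-48 months as median | 12 months | 0.8-1.6 | 0.8-2.8 |
| 36-48 months as mean (medians 25.0-33.3) | 6-24 months | 0.7-3.3 | 0.7-5.4 |

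For the second row the standard error at n = 46 is 2.4-3.7 points. Section 8.2 gives a total of 64 instead; there it is smaller by √(46/64) = 0.85, about 2.0-3.1 points. The overstatement stays below one standard error in both cases.

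**Null case.** If deaths occur before progression at the same rate as after it, the bias is 0.0. If mortality were lower after progression, its sign would reverse.

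**The case against.** The strongest reply is that bias needs two conditions, and the documents state neither. Section 8.1 never says that survival ascertainment stops, and 10.3 uses mandatory language about continuing. That stands: what the text establishes is an unreconciled conflict and an undefined period, not a biased result. It does not remove the need to settle the matter, because no section supplies the missing instruction.

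The data may also exist elsewhere. Section 14.0 places study data in EPIC and OnCore, Appendix II mentions subject status in OnCore, and inclusion criterion 2 requires participation in the Iowa Neuroendocrine Tumor Registry. These are real candidates. None is stated to record deaths after removal, and none is tied to 12.1.

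Overall survival is descriptive and absent from the objectives in section 4. That also stands, and it keeps the point minor.

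Three stronger readings are tempting and not supported:
- A reader might infer that the 6-month censoring sentence itself biases the curve. It is an administrative cut-off and does not. Nor is any defect shown in the time-to-progression rule.
- A reader might take the 7-month upper end of the comparator-drug range in 1.4 as this trial's time to progression. That gives 2.3-8.2 points at 6 months after Cycle 3, and up to about 12 at the far end of the window. The documents do not give that figure for this treatment, so it is no basis for the estimate. Faster-progressing tumors are eligible, but their share is not stated.
- A reader might infer that the trial's main conclusion is at risk. The two-stage decision rests on CR, PR and SD and does not use survival.

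**Conclusion.** The concern holds in conditional form. Sections 8.1 and 10.3 must be reconciled, and no available section continues vital status after removal at progression. If removal ends ascertainment and mortality is higher after progression, overall survival is overstated by about 0.5-2.4 points at 6 months after Cycle 3 and 0.5-4.0 points across the 6-9 month window.

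These figures rest on exponential times, on reading 36-48 months as a median, and on an assumed 6-24 month median survival after progression. Assuming no deaths before progression pushes the estimate up. The direction is more secure than the size. This is a minor, inexpensive correction to a descriptive secondary analysis.

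**What to change.** 1. Reconcile 8.1 with 10.3 and define the long-term follow-up period. State that removal at progression ends study assessments but not vital-status follow-up, which continues through the time of the 6-9 month visit.
2. Add to 12.1: overall survival counts death from any cause, regardless of progression or removal, and subjects not known to have died are censored at the date last known alive.
3. Name the source: the medical record, OnCore status or the tumor registry if confirmed to record death, or a brief contact. Calendar footnote 11 lets local physicians do the 3-4 month follow-up, so a check of the institution's own record alone may miss deaths.

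Items 1 and 2 should be made together. The time-to-progression rule and the imaging schedule need no change. The cost is text edits, modest record checking or contact, and possibly a change to consent or IRB wording (the consent pages are not in our copy). If the two conditions hold, the survival estimate will be slightly less favourable.

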8.2 Stopping Rules for Trial

Enrollment will proceed according to a Simon two-stage study design. Thirty-five subjects will be enrolled in the first stage; if 5 or fewer patients respond (Stable, PR or CR) as determined by ⁶⁸Ga-DOTATOC PET/CT and diagnostic CT or MRI (RECIST 1.1 criteria), the study will be closed and the treatment ruled clinically uninteresting. Otherwise, an additional 29 subjects will be enrolled. If 20 or more responses are observed in the total of 64 subjects, then the treatment will be ruled worthy of further study.

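### Section 12.2 counts renal toxicity at Grade 4 or above but other toxicity only at Grade 4, so fatal non-renal toxicities fall outside the written stopping count

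*Combined protocol and SAP*

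**What the plan says.** Monitoring toxicity is Primary Objective 2 (section 4.1), and section 12.2 sets the rule for stopping the trial on it. The first trigger reads "If four or more subjects experience renal toxicity", followed by a greater-than-or-equal sign and Grade 4. The second reads "If any other irreversible Grade 4 toxicity is observed in four or more subjects". If either is met, the treatment is declared too toxic and stopped.

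Section 12.2 closes with "Adverse events will be graded according to the most recent CTE guidelines". Section 9.1 instead names the "Common Terminology Criteria for Adverse Events version 4.0 (CTCAE v4.0" edition as the grading standard.

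Section 8.2, headed as the stopping rules for the trial, contains only the two-stage response rule. It also uses different sizes from 12.1. Section 8.2 has "Thirty-five subjects will be enrolled in the first stage; if 5 or fewer patients respond" and "If 20 or more responses are observed in the total of 64 subjects". Section 12.1 has "Sixteen (16) subjects will be enrolled in the first stage; if 7 or fewer patients respond" and "If 24 or more responses are observed in the total of 46 subjects".

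Appendix II requires serious adverse events, deaths among them, to be reported to the DSMC whatever their attribution, within a defined window. It also has monitors compare cumulative reports with the stopping rules. Section 8.1 lists termination by the sponsor among the reasons for leaving the study.

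**The concern.** Two adjacent sentences that do the same job use different grade limits. The authors wrote the open-ended limit for the kidney and did not repeat it for other organs. Nothing explains the difference, so it looks like a drafting slip.

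Non-renal harm is not remote in the document's own terms. Section 9.2 lists reduced red cells, white cells and platelets, and two cases of myelodysplastic syndrome among more than 2500 treated patients. Section 9.0 calls the trial risk level 4, which Appendix II defines as a risk of treatment-related death above 5% or of Grade 4-5 serious events above 5%. If non-renal deaths do not count, a decision to stop because of them rests on discretion and not on the prespecified rule.

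The grading mismatch matters less. It leaves open which edition decides whether an event reaches the triggering grade.

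**Working it through.** **What each trigger counts.** Assume that an event is classified by its worst grade, that Grade 5 is the fatal grade, and that 'any other' toxicity is pooled across types (12.2 does not say whether it is pooled or counted per type).

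| Events observed | Renal trigger | Non-renal trigger, as written |
|---|---|---|
| 4 subjects, renal, Grade 4 | met | not applicable |
| 4 subjects, renal, Grade 5 | met | not applicable |
| 4 subjects, non-renal, irreversible Grade 4 | not applicable | met |
| 4 subjects, non-renal, Grade 5 | not applicable | not met |
| 3 subjects, non-renal, irreversible Grade 4, plus any number at Grade 5 | not applicable | not met |

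In the fourth row the probability of triggering is 0 at any true rate, because no event of that kind enters the count. The rule also runs the wrong way: a subject whose irreversible Grade 4 toxicity becomes fatal moves from counted to not counted.

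**Does another section fill the gap?** Section 8.2 contains only response counts. Section 8.1 lets the sponsor terminate the study but sets no number. Appendix II sends deaths to the DSMC and tells monitors to compare with the stopping rules; the rule they would consult is the one in 12.2. No other numeric toxicity rule appears.

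**Grading standard.** Section 9.1 fixes one version. Section 12.2 gives no version, and its abbreviation CTE is undefined; it may be a slip for CTCAE or CTEP, both of which appear in section 9. The documents do not show any Grade 4 definition that differs between versions.

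**Behaviour of the existing count (optional).** The plan states no tolerable toxicity rate and no operating characteristics for this rule, so it has no figure to reproduce. The true rates p below are assumptions. For one trigger and n subjects:

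P(X ≥ 4) = 1 − Σ (k = 0 to 3) C(n, k) pᵏ (1 − p)ⁿ⁻ᵏ

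For n = 46 and p = 0.05 the four terms are 0.0945, 0.2287, 0.2708 and 0.2091. They sum to 0.8031, so P = 0.197.

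| Assumed true rate | n = 46 (12.1) | n = 64 (8.2) |
|---|---|---|
| 5% | 0.197 | 0.399 |
| 10% | 0.688 | 0.894 |
| 20% | 0.989 | 0.9995 |

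The choice between 46 and 64 matters most at low rates: at 5% the chance of reaching four roughly doubles. As a check on the denominator, the 12.1 response design recomputes to an early-termination probability of 0.716 (stated 0.72), power of 0.801 (stated 0.80) and type 1 error of 0.049 (stated 0.05). So 46 belongs to a coherent design, but 64 still stands in 8.2 and 12.4.

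**The case against.** The strongest reply is that oversight does not depend on this sentence. Serious events within the reporting window reach the DSMC quickly, monitoring takes place at least twice a year, and the sponsor can end the study. A numeric rule also does not forbid an earlier stop, and a sensible committee would count a death. This stands in part. A reader might infer that four non-renal deaths would leave the trial running. The documents do not support that; they support only that such deaths would not trigger the written count.

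A reader might also infer that the grading mismatch lets the triggering grade change during the trial. That is possible but not shown, so it remains a minor ambiguity.

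Finally, a reader might infer that a flat count of four is too slow and that an earlier threshold, such as three within the first 16, is needed. The arithmetic is real: at an assumed 20% rate, the chance of stopping by subject 16 rises from 0.402 to 0.648. The documents do not support the conclusion, for four reasons:

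- They state no unacceptable rate, so a needed stop cannot be defined, and nothing in them points to 20%.
- The figures take each outcome as known before the next subject enters, although cycle 3 falls in weeks 13-17 and section 9.2 says kidney damage may appear months after the last dose.
- At an assumed 5% rate, stopping by subject 16 would rise from 0.7% to 4.3%.
- The first-stage size is 16 in 12.1 but 35 in 8.2.

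Whether to add an early threshold is a trade-off for the sponsor, not an error in the plan.

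**Conclusion.** The non-renal trigger is wrong as written. It omits Grade 5 events that the renal trigger includes, and no other numeric rule covers them. The size is categorical: fatal non-renal toxicities contribute nothing to the count at any true rate. This rests on the literal wording and on classifying events by worst grade. Reporting to the DSMC and the sponsor's power to terminate limit the practical harm but do not repair the rule.

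The conflict over the grading standard is real and minor. The probabilities for the count of four describe the existing rule under assumed rates and a single pooled trigger; they are not evidence that four is the wrong number.

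**What to change.** 1. Reconcile the two trigger sentences in 12.2 so that Grade 5 events count in the non-renal trigger as they already do in the renal one. This needs only a change to the grade limit. The rule would still be confined to toxicities, so deaths from other causes would not be drawn in.
2. Reconcile 9.1 and 12.2 so that both name the same grading standard and version.
3. Optional: state the operating characteristics of the existing count of four over a range of true rates labelled as assumed, and say whether non-renal toxicities are pooled or counted by type. The stage sizes and total in 8.2, 12.1 and 12.4 need to be reconciled first, because the figures depend on them.

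Items 1 and 2 are wording amendments with no effect on sample size or on the response analysis. The first can only add events to the non-renal count, which is its purpose. Item 3 costs a short table.
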